5.3 General Concomitant Medication and Supportive Care Guidelines

No clinical drug drug interactions with ublituximab or umbralisib have been reported to date and thus there are no specific prohibited concomitant medications based on potential for drug drug interactions. Supportive medications in accordance with standard practice (such as for emesis, diarrhea, etc.) are permitted and patient should receive full supportive care during study participation (including fluids and electrolyte replacement, and antibiotics when appropriate). Use of myeloid growth factors or red blood cell growth factors (erythropoietin) is permitted per institutional policy. Transfusions may be given in accordance with institutional policy. After consultation with the Sponsor the following may be considered; localized hormonal or bone sparing treatment for non-B-cell malignancies. Short courses (≤ 14 days) of steroid treatment for non-cancer related medical reasons (i.e., joint inflammation, asthma exacerbation, rash, antiemetic use and infusion reactions) at doses that do not exceed 60 mg per day of prednisone or equivalent are permitted. Treatment for autoimmune cytopenias are permitted for < 14 days at doses that do not exceed 60 mg per day of prednisone or equivalent, IVIG will be allowed for immune mediated platelet or red cell destruction or for hypogammaglobulinemia and infection risk. IVIG may not be given on the same day as ublituximab.

Prophylactic antibiotics against *Pneumocystis jiroveci* pneumonia (PJP) should start prior to starting umbralisib. All subjects should also be prophylaxed against herpes zoster virus with famciclovir, valacyclovir or acyclovir. Dapsone 100mg daily is recommended for PJP prophylaxis, but the agents of choice for antibiotic prophylaxis is left to investigator discretion. Standard dosing for prophylactic purposes should be followed for each respective required antibiotic.

Any non-study protocol related chemotherapy, anti-cancer immunotherapy, experimental therapy, or radiotherapy are prohibited while the subject is on protocol except as outlined above.

5.4 Duration of Therapy and Criteria for Removal from Study

In the absence of treatment delays due to adverse event(s) greater than 8 weeks from scheduled dose, combination treatment may continue for 6 months followed by at least 18 months of

umbralisib monotherapy. Patients deriving benefit at 2 years will be allowed to continue on study drug. If a subject meets the following criteria, they will be removed from study treatment:

- Disease progression
- Failure to achieve \geq PR to combination therapy (See section 5.4.1)
- Intercurrent illness that prevents further administration of both study drugs
- Unacceptable adverse event(s)
- Patient decides to withdraw from the study, or
- General or specific changes in the patient's condition render the patient unacceptable for further treatment in the judgment of the investigator

5.4.1 Procedures for Subject Removal if Less Than PR at Completion of Combination Therapy

Subjects will be evaluated for objective response after completion of 6 cycles of combination therapy ublituximab and umbralisib (i.e. C7D1 radiographic evaluation and clinical and laboratory assessment). Subjects with a response \geq PR will be allowed to continue onto the umbralisib monotherapy maintenance portion of the study. Subjects not meeting at least the PR response definition outlined in Section 9.1.2 at the C7D1 study visit will be removed from study with the following exception;

If a subject has stable disease, is deriving clinical benefit per investigator assessment, and for whom an approved therapy with known efficacy is not available (i.e. double refractory to BTKi or Bcl2 inhibitor) those subjects will be allowed to continue on study and proceed with umbralisib monotherapy.

All subjects will be allowed to start C7D1 and continue on study for up to 3 cycles as complete response assessment data may not be readily available to make clinical decisions and arrangement of subsequent therapy may take additional time to ensure safe transition of subjects to alternative treatments. This is to prevent abrupt removal of subjects from therapy and to allow sufficient time for data to be evaluated in an objective manner. All subjects must be assessed by the investigator for suitability to continue on umbralisib monotherapy prior to C10D1. Effort must be made by investigator to expeditiously make response assessment and arrange for alternative management at the earliest timepoint prior to C10D1. No subject meeting criteria outlined in this Section 5.4.1 will be allowed to continue on study beyond C10D1.

5.5 Duration of Follow Up

The anticipated duration of patients on study therapy will be 2 years though patients deriving benefit will be allowed to continue on study beyond two years. Patients removed from study for unacceptable adverse events will be followed until resolution or stabilization of the adverse event even if that period is longer than 30 days after removal.

After withdrawal from protocol treatment, all patients should be followed for AEs for 30 calendar days after their last dose of either study drug. All new AEs occurring during this period

must be recorded and followed until resolution, unless, in the opinion of the investigator, these values are not likely to improve because of the underlying disease.

Subjects who discontinue study treatment for reasons other than disease progression or withdrawal of consent will be followed for progression free survival and survival every 3 months until documentation of disease progression, death or initiation of CLL directed non study treatment.

Visits for subjects with early treatment discontinuation other than disease progression, death or withdrawal of consent, will continue for 3 months after study drug discontinuation. Subjects and study team should collect the following data during this follow-up period:

- ECOG
- Medical history
- Physical exam
- Vital Signs
- Weight
- CBC with differential
- CMP
- CT neck, chest, abdomen and pelvis with contrast every 12 months or as clinically warranted to document disease progression

Subjects who discontinue therapy for any reason except withdrawal of consent will be followed for overall survival for up to 5 years. Survival follow-up will be documented by either chart review if the subject remains an active patient in the investigators clinic or by phone call every 6 months up to 5 years. If subject is not in active follow-up then a chart note should be placed within the patient chart to confirm survival status.

When the first subject enters year five of treatment or follow-up the study may be amended to address continuation of study therapy or follow-up beyond year 5.

6. Dosing Delays/Dose Modifications

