1.3 Exploratory Objectives

Exploratory Objectives: Progression free survival (PFS) and overall survival will be exploratory objectives. We will also be collecting samples for future use in research as yet undetermined subject to review and approval by TG Therapeutics, Inc. Potential correlative studies may evaluate molecular predictors of response or resistance, changes in immune profile, and clonal evolution patterns in patients exposed to U2.

2. Background

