9.3. Progression-Free Survival

Progression-free survival is defined as the interval between the first treatment day to the first sign of disease progression or death.

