11.2.2 Analysis of Secondary and Exploratory Endpoints

Analysis of outcomes will remain descriptive. With 12 patients enrolled in Cohort A, an exact binomial (Clopper-Pearson) 95% confidence interval for the CR rate can be constructed to have a width of approximately 46.3% (2.1%, 48.4%). This calculation assumes that the CR rate will approach 16.7% in cohort A. Similarly with 12 patients enrolled in cohort B, and exact binomial (Clopper-Pearson) 95% confidence interval for the CR rate can be constructed to have a width of approximately 38.5% (0.2%, 38.5%). This calculation assumes the CR rate will approach 8% in cohort B. Assuming adequate follow-up time, Kaplan-Meier survival analysis will be used to assess DoR, PFS, and OS, in the entire cohort. All p-values will be two-sided with statistical significance evaluated at the 0.05 alpha level. Ninety-five percent confidence intervals for median DoR/PFS/OS-time and DoR/PFS/OS proportions, will be calculated to assess the precision of the obtained estimates. Safety will be collected and adverse events will be tabulated per incidence of specific AE terms will be reported for the entire cohort. All analyses will be performed in SAS Version 9.4 (SAS Institute, Inc., Cary, NC) and Stata Version 15.0 (StataCorp, College Station, TX).

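### Exploratory PFS: no rule covers stable-disease subjects removed for less than PR who then start other CLL therapy, so the natural Kaplan-Meier analysis censors them for a reason tied to poor response

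*Combined protocol and SAP*

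**What the plan says.** Five parts of the protocol meet here.

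- **Removal (5.4.1).** "Subjects not meeting at least the PR response definition outlined in Section 9.1.2 at the C7D1 study visit will be removed from study", with one exception: stable disease, clinical benefit in the investigator's judgement, and no approved therapy of known efficacy, with double-refractory disease given as the case in point. Of these it says "those subjects will be allowed to continue on study and proceed with umbralisib monotherapy".
- **Timing (5.4.1).** For the others the investigator is to "arrange for alternative management at the earliest timepoint prior to C10D1", which is also the latest time such a subject may remain on study.
- **End of progression follow-up (5.5).** Subjects who stop for reasons other than progression or withdrawn consent are followed for PFS "until documentation of disease progression, death or initiation of CLL directed non study treatment". Survival status is collected for up to 5 years, by chart review or six-monthly calls.
- **Endpoint (9.3).** PFS is "the interval between the first treatment day to the first sign of disease progression or death". Start of another therapy is not an event, and no censoring rule is given.
- **Analysis (11.2.2).** "Kaplan-Meier survival analysis will be used to assess DoR, PFS, and OS, in the entire cohort". Section 1.3 makes PFS exploratory.

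**The concern.** A subject with stable disease at C7D1 who falls outside the exception is taken off study treatment, moved to another therapy within about three cycles, and no longer assessed for progression once that therapy starts. At that point there is no PFS event and nothing further to observe, so the ordinary Kaplan-Meier treatment is censoring at the switch.

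Kaplan-Meier assumes that a censored subject has the same later risk as those still under observation. Here the protocol itself causes the censoring, through failure to reach PR, and those left at risk are mainly responders. If stable-disease subjects would progress sooner than responders, the PFS proportions and median are too favourable. With 24 subjects, two or three such censorings are visible in the curve. Because no rule is written, its handling could also be chosen after the data are seen.

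**Working it through.** The plan states no PFS assumption, so there is no PFS figure to reproduce. Its ORR intervals do reproduce with n = 12 and the non-integer counts 6.6 and 4.8 (25.0–82.5% and 14.1–70.9%). That confirms the assumed rates of 55% and 40%, which are used below.

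**From the documents**
- Below PR: 0.45 × 12 = 5.4 in cohort A and 0.60 × 12 = 7.2 in cohort B, so 12.6 of 24. Responders: 11.4/24 = 0.475.
- With the lead-in cycle and 28-day cycles, C7D1 falls after 7 × 28 = 196 days (6.44 months) and C10D1 after 10 × 28 = 280 days (9.20 months).
- Section 11.1 expects close to 90% of cohort B to be double refractory.

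**Assumed, because the documents give nothing**
- A share s = 33–67% of non-responders have stable disease at C7D1. The rest have progressed by then and count as events.
- Median time from C7D1 to progression is m = 3–6 months for stable disease and 24 months for responders.
- Switches are spread evenly from C7D1 to C10D1.
- Exception scenario: 90% of cohort B stable-disease subjects and none in cohort A are kept, so the removed fraction is (5.4 + 0.1 × 7.2)/12.6 = 0.486.

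**PFS at 18 months had nobody switched** (18 − 6.44 = 11.56 months after C7D1)

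0.475 × 2^(−11.56/24) + 0.525 × s × 2^(−11.56/m)

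For s = 50%:
- m = 3: 0.475 × 0.716 + 0.2625 × 0.069 = 35.8%
- m = 6: 0.475 × 0.716 + 0.2625 × 0.263 = 40.9%

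**Large-sample Kaplan-Meier value with censoring at the switch**

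At u months after C7D1, let R, K and C be the proportions at risk who are responders, kept stable-disease subjects, and removed stable-disease subjects not yet switched. C carries the factor 1 − u/2.76 and is zero from C10D1. With hazards λR = ln2/24 and λS = ln2/m,

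h(u) = [λR·R + λS·(K + C)] / (R + K + C), and PFS(18) = (0.475 + 0.525s) × exp(−∫h du) over 11.56 months.

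Cohort A alone uses 0.55 and 0.45 in place of 0.475 and 0.525. Differences were taken before rounding.

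| s, m | Pooled, no switch | Pooled KM, exception as above | Pooled KM, exception never used | Cohort A alone, no exception: no switch → KM |
|---|---|---|---|---|
| 33%, 3 | 35.2 | 38.7 (+3.5) | 43.4 (+8.2) | 40.4 → 47.5 (+7.0) |
| 33%, 6 | 38.6 | 41.3 (+2.7) | 45.0 (+6.4) | 43.3 → 48.9 (+5.5) |
| 50%, 3 | 35.8 | 40.8 (+4.9) | 47.9 (+12.1) | 40.9 → 51.4 (+10.5) |
| 50%, 6 | 40.9 | 44.7 (+3.8) | 50.5 (+9.5) | 45.3 → 53.5 (+8.2) |
| 67%, 3 | 36.4 | 42.6 (+6.2) | 52.4 (+15.9) | 41.5 → 55.3 (+13.8) |
| 67%, 6 | 43.2 | 47.9 (+4.7) | 55.9 (+12.6) | 47.3 → 58.2 (+10.9) |

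In the exception scenario about 1.5 to 3.5 of 24 subjects are censored for this reason.

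**Three checks**
- *Equal hazards* (m = 24, s = 50%): both values are 52.8%, so the bias is zero.
- *Progression counted regardless of next therapy* (s = 50%, m = 3, exception scenario, assumed median of 30 months on next therapy): the average over switch times of 2^(−u/3) × 2^(−(11.56−u)/30) is 0.583. PFS is then 0.340 + 0.2625 × 0.514 × 0.069 + 0.2625 × 0.486 × 0.583 = 42.4%, against 40.8% with censoring. The sign reverses.
- *Switch counted as an event* (s = 50%): 34.0% if the exception is never used (0.475 × 0.716), and 35.0–37.6% in the exception scenario, against a no-switch value of 35.8–40.9%. This lies below the no-switch value, so it is a bound and not a correction.

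**The case against.** A reader might infer that the rules as written censor every subject below PR and inflate PFS by 6 to 16 points. The documents do not support that.

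- Censoring at new therapy is inferred from when follow-up stops; no section prescribes it.
- Subjects who have progressed by C7D1 are events. Only stable-disease subjects outside the exception who switch before progressing are affected.
- The 6 to 16 points require the exception never to be used, although most of cohort B is expected to be double refractory. With 90% of cohort B stable-disease subjects kept, the figure falls by more than half. That 90% is generous, since clinical benefit is also required.
- Deaths after new therapy are still collected and could count under Section 9.3.
- Direction and size rest on assumed hazards and on which PFS is meant.
- PFS is exploratory and descriptive. At a PFS near 40% with 24 subjects, the 95% half-width is about 1.96 × √(0.4 × 0.6/24) = 20 points, several times the exception-adjusted bias.

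All of this stands, and it limits the point without removing it. Later deaths do not recover unobserved progressions. The exception is unlikely to help cohort A subjects who have not had venetoclax, because the Protocol Summary describes that drug as effective after BTKi resistance and approved after one prior line. Wide intervals do not excuse an avoidable shift in one direction.

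**Conclusion.** The point holds as a minor one. The plan loses later progressions in non-exempt stable-disease subjects for a reason tied to poor response, mainly in cohort A, and says nothing about how Kaplan-Meier should treat them. If those subjects would progress sooner than responders, exploratory PFS is overstated.

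Under the stated assumptions the 18-month overstatement is about 3 to 6 points pooled with the exception used for 90% of cohort B stable disease, and about 5 to 14 points in cohort A alone without it. The pooled range of 6 to 16 points applies only if the exception is never used. The progression rates are assumptions throughout, and the primary ORR analysis is untouched.

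**What to change.** 1. State that the main PFS analysis keeps the Section 9.3 definition and censors at the start of non-study CLL therapy.
2. Pre-specify a sensitivity analysis that counts the start of such therapy after removal for less than PR as an event, labelled as a conservative lower bound.
3. Report both side by side, with the number censored for this reason in each cohort.
4. Record the date of next therapy, and any progression or death, from the chart review or calls already planned for survival.

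Three pairs of passages that decide who is followed should also be reconciled: Section 5.2 (removal at C7D1) with the 5.4.1 exception; the two visit durations in Section 5.5 (every 3 months until an endpoint, and for 3 months after discontinuation); and the Table 1 footnote, which names toxicity discontinuations only, with the broader group in Section 5.5.

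The cost is one extra Kaplan-Meier run, a few date fields, and a less favourable PFS figure beside the main one. No treatment rule, visit or sample size needs to change for items 1 to 4.

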5.1 Schedule of Evaluations

Table 1. Schedule of trial events

Schedule of Assessments				Year 1										
Study Procedure	Screening	C-1	C-1	Cycle 1				C2 D1	C3 D1	C4 D1	C5 D1	C6 D1	C7 D1	C10 D1
		D1	D15	Day 1	Day 2	Day 8	Day 15							
Informed Consent	X													
Inclusion/Exclusion	X													
ECOG	X	X	X	X				X	X	X	X	X	X	X
Demographics	X													
Medical History	X	X	X	X	X	X	X	X	X	X	X	X	X	X
Physical Exam	X	X	X	X	X			X	X	X	X	X	X	X
Vital Signs	X	X	X	X	X	X	X	X	X	X	X	X	X	X
Height	X													
Weight	X	X	X	X				X	X	X	X	X	X	X
EKG	X													
Bone Marrow Biopsy	X													
Bone Marrow Aspirate	X													
CBC with diff	X	X	X	X	X	X	X	X	X	X	X	X	X	X
Serum Chemistry (CMP) ^a	X	X	X	X	X	X	X	X	X	X	X	X	X	X
HIV Rapid Screen	X													
Hepatitis Antibody Screen ^b	X													
Cytomegalovirus (CMV) PCR	X										X			X
B-HCG ^c (FCBP only)	X													
Circulating DNA (research)		X		X				X						X
Clonal Evolution Analysis (research)		X		X				X						X
Ublituximab Infusion			X	X	X	X	X	X	X	X	X	X	X	
Umbralisib Dispensation		X	X	X				X	X	X	X	X	X	X
Adverse Event Monitoring ^d	At each timepoint AEs will be collected													
Radiologic Evaluation ^e	X							X						X

Schedule of Assessments	Year 2				Year 3+	EOT	Follow-up*
Study Procedure	C13 D1	C16 D1	C19 D1	C22 D1	C25 D1 then Every 3 months	30 days post last dose	Every 3 months
Informed Consent							
Inclusion/Exclusion							
ECOG	X	X	X	X	X	X	X
Demographics							
Medical History	X	X	X	X	X	X	X
Physical Exam	X	X	X	X	X	X	X
Vital Signs	X	X	X	X	X	X	X
Height							
Weight	X	X	X	X	X	X	X
EKG							
Bone Marrow Biopsy							
Bone Marrow Aspirate							
CBC with diff	X	X	X	X	X	X	X
Serum Chemistry (CMP) ^a	X	X	X	X	X	X	X
HIV Rapid Screen							
Hepatitis Antibody Screen ^b							
Cytomegalovirus (CMV) PCR	X	X	X	X	X		
B-HCG ^c (FCBP only)							
Circulating DNA (research)	X		X		X	X	
Clonal Evolution Analysis (research)	X		X		X	X	
Ublituximab Infusion							
Umbralisib Dispensation	X	X	X	X	X		
Adverse Event Monitoring ^d	At each timepoint AEs will be collected						
Radiologic Evaluation ^e	X		X				X (q12mo)

Footnotes:

- * Subjects who discontinue treatment due to toxicity, but have not progressed will continue in study follow-up. Visits should occur q3months after EOT visit or until subsequent non-study drug administration. Patients who discontinue treatment due to progression of disease will enter survival follow-up. Survival follow-up will be documented by phone call every 6 months up to 5 years.

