- a. CMP includes a Basic Metabolic panel (Sodium, potassium, chloride, bicarb, blood urea nitrogen, creatinine, calcium, glucose) and a Hepatic function panel (protein total, albumin, globulin, alanine aminotransferase, aspartate aminotransferase, total bilirubin, alkaline phosphatase), Uric acid required only at screening, C-1 D1, C-1 D15, C1 D1, and C1 D2.
- b. Hepatitis antibody screening will consist of Hepatitis A ab, HBsAg, HBcAb, Hepatitis C Ab. If HBcAb is positive, an HBV DNA PCR should be performed.
- c. B-HCG pregnancy testing required only for females of child bearing potential (FCBP). At screening should be tested by serum within 3 days prior to C-1 D1.
- d. Adverse events should be assessed up to 30 days post last dose. For all serious adverse events (SAE), concomitant medications should be assessed and appropriately captured/reported.
- e. CT neck, chest, abdomen, pelvis with contrast. Radiologic evaluation during follow-up should occur every 12 months or as clinically warranted to document disease progression.

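### Section 5.5 gives two follow-up durations for subjects who stop treatment without progression; if the 3-month one is applied, later progressions may be missed or dated late for DoR and PFS

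*Combined protocol and SAP*

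**What the plan says.** Two consecutive paragraphs of Section 5.5 cover essentially the same subjects.

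- **First paragraph.** Subjects who stop for reasons other than progression or withdrawal of consent are to be "followed for progression free survival and survival every 3 months until documentation of disease progression, death or initiation of CLL directed non study treatment".
- **Second paragraph.** "Visits for subjects with early treatment discontinuation other than disease progression, death or withdrawal of consent" are said to be ones that "will continue for 3 months after study drug discontinuation". A list of data for this period follows: performance status, history, exam, vital signs, weight, blood count, chemistry and "CT neck, chest, abdomen and pelvis with contrast every 12 months or as clinically warranted to document disease progression".

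Table 1 in Section 5.1 has a follow-up column headed every 3 months, with imaging every 12 months. Its starred footnote says "Subjects who discontinue treatment due to toxicity, but have not progressed will continue in study follow-up" and "Visits should occur q3months after EOT visit or until subsequent non-study drug administration". Footnote e adds: "Radiologic evaluation during follow-up should occur every 12 months or as clinically warranted to document disease progression".

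Section 5.5 also provides survival follow-up for up to 5 years, by chart review or a call every 6 months. It asks for survival status and does not mention progression.

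**The concern.** The two paragraphs of Section 5.5 cannot both be followed. Study staff who take the second as the visit rule would schedule nothing after month 3 except survival contacts.

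DoR is a secondary objective and PFS an exploratory one. Sections 9.2 and 9.3 define both by the date of progression. Under Section 9.1.3 that date can come from lymphocyte counts, nodes, liver or spleen, so the exams and blood counts that would stop are themselves means of detecting progression, as are the CTs.

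Stopping without progression is foreseen by the design. Table 4 requires discontinuation for several toxicities and for delays over 56 days. Section 5.4.1 takes subjects with less than PR at C7D1 off, with an exception for some with stable disease. A progression date that nobody looked for may not be recoverable later.

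**Working it through.** The plan states no figure on this point, so the main check is a comparison of texts.

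**1. Rules side by side**

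| Source | Who | Visits | Visits end at | CT |
|---|---|---|---|---|
| 5.5, first paragraph | stopped, not for progression or withdrawal | every 3 months | progression, death or new CLL therapy | not stated |
| 5.5, second paragraph | stopped early, not for progression, death or withdrawal | interval not stated | 3 months after stopping | every 12 months or as warranted |
| Table 1 column and footnotes | stopped for toxicity, not progressed | every 3 months after the end-of-treatment visit | non-study drug | every 12 months or as warranted |

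Only the second paragraph of 5.5 has a 3-month end, and it conflicts with its own CT interval. The Table 1 footnote has separate gaps: it names only toxicity stops, and it omits progression and death as end points.

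**2. What is lost under the 3-month reading**

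Take a subject who stays progression-free for 24 months after stopping, counting from the stop.

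- Every 3 months: 24/3 = 8 visits and 24/12 = 2 routine CTs.
- For 3 months: 3/3 = 1 visit and no routine CT, because 3 < 12.

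**3. How much progression could fall after month 3 (illustration)**

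The documents give no time from stopping to progression. Assume it is exponential with median m months, so S(t) = 2^(−t/m). The share progressing within 3 months is 1 − 2^(−3/m). Of progressions within 24 months, the share after month 3 is [2^(−3/m) − 2^(−24/m)] / [1 − 2^(−24/m)].

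| Assumed m (months) | Progress within 3 months | Of 24-month progressions, after month 3 |
|---|---|---|
| 6 | 29% | 69% |
| 12 | 16% | 79% |
| 18 | 11% | 82% |
| 24 | 8% | 83% |

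For m = 12: (0.841 − 0.250)/0.750 = 0.788. These shares fall outside the scheduled visits; they are not shares certain to be missed.

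**4. Weight of one responder**

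Inputs from Section 11: 12 subjects per cohort, with anticipated ORR of 55% (A) and 40% (B).

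- Cohort A: 12 × 0.55 = 6.6 responders; 1/6.6 = 15%.
- Cohort B: 12 × 0.40 = 4.8 responders.
- Pooled: 6.6 + 4.8 = 11.4; 1/11.4 = 9%.

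Both weights are given because Section 11.2.2 plans Kaplan-Meier analysis in the entire cohort, which may mean pooled.

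**5. What is not touched**

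The Clopper-Pearson intervals for ORR recompute to 24.96% to 82.54% (A) and 14.06% to 70.94% (B), matching the plan. They do not depend on follow-up after stopping.

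**The case against.** The strongest reply is that this is a slip of wording. The preceding paragraph, the Table 1 column, both footnotes and the 12-monthly CT in the sentence's own list all point to visits *every* 3 months. The statistical section describes a single-center trial, so the misreading is less likely than across many sites. Outcome analysis is descriptive, and only a secondary and an exploratory endpoint are involved. All of this stands. It limits the weight of the point but does not remove the contradiction, because the sentence is the one in Section 5.5 that says how long visits last.

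A reader might infer more than the documents support:

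- **That the 3-month sentence governs.** Nothing ranks it above the preceding paragraph or Table 1, and the requirement that subjects "will be followed for progression free survival and survival every 3 months until documentation of disease progression" remains in force beside it.
- **That subjects would be censored at 3 months, leaving DoR and PFS to describe mainly those who tolerate treatment.** The plan states no censoring rule. Progressions within 3 months would be recorded, and clinically warranted CTs or chart review could reveal some later ones.
- **That the absence of an early off-treatment scan is peculiar to the 3-month reading.** Under the other rule, too, the first routine CT may be up to 12 months away. The 3-month reading loses the later exams and labs, and the yearly CTs.
- **That a set number per cohort would be lost.** An assumed toxicity stop rate of 20–30% would give 2.4–3.6 of 12, but the documents contain no such rate. Some of those subjects would progress, die or start new therapy within 3 months anyway.

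**Conclusion.** The contradiction is real and should be corrected. Section 5.5 gives incompatible visit durations for essentially the same subjects, and the 3-month version also conflicts with its own CT item and with Table 1. The likeliest explanation is *for* written in place of *every*, but the current text does not say so.

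The consequence is conditional. Only if the 3-month sentence is applied does scheduled detection of progression stop at month 3, with DoR and PFS exposed to missed or late-dated events. ORR and CR rate are unaffected, and OS has its own 5-year follow-up. The total effect cannot be sized, because the number stopping without progression is not given. The 15% and 9% weights per responder rest on the plan's anticipated response rates. The 69–83% range rests on the assumed exponential medians of 6 to 24 months.

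**What to change.** Reconcile the passages in one amendment.

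1. In Section 5.5, replace the 3-month sentence with: *Visits for subjects who discontinue treatment without progression will continue every 3 months after study drug discontinuation until documented progression, death, withdrawal of consent or start of non-study CLL therapy.* Keep the listed assessments.
2. Rewrite the starred Table 1 footnote to cover the same population (all who stop without progression, not only for toxicity) and the same four end points. Changing *or until* to *until* would not be enough, since it leaves the narrower population and the missing end points in place.

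The cost is one sentence and one footnote. No visits or scans are added beyond those that the preceding paragraph and Table 1 already plan.
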